Protocol Title: A Cross-over Pilot Trial to Determine the Effect of an LSU Patented Dietary Herbal Supplement on Quality of Life

PI Name: **[name]**

Sub-Investigator's Name(s): **[name]**

Protocol Version Date: **December 16, 2021**

IRB Review History

Modification 3

Objectives

Specific Aim 1: Compare the quality of life using the validated Chubon Quality of Life Rating scale after taking the supplement or the placebo at baseline followed by a 2-week washout, then 1 week taking the supplement or placebo that was not taken in the first period.

Specific Aim 2: Compare the safety of the supplement by evaluating questionnaires, chemistry panel, CBC, Janus 3, adverse events and polysomnography at baseline and after 1 week of nightly administration with the supplement or the placebo before and after a 2-week washout.

Hypothesis: The supplement will improve the quality of life compared to the placebo condition

Background

[name] and [name] at Louisiana State University Agricultural Center developed a novel dietary herbal supplement consisting of at least two components chosen from the following six foods. 1. Collagen peptides of less than 3500 Daltons and preferably less than 2,000 Daltons derived from animals like cows, or other glycine-rich peptides. 2. Theanine, a component of decaffeinated green tea. 3. lactucopicrin, deoxylactucopicrin or another lactucopicrin derivative found in chicory. 4. Hyaluronic acid, a component of cartilage. 5. epigallocatechin gallate, a component decaffeinated green tea. and 6. quinic acid found in chicory. This dietary supplement contains chicory and decaffeinated green tea containing epigallocatechin gallate. These ingredients are thought to decrease Janus kinase 3 (JAK-3) and people who have tried the supplement claim that it made them feel better, made them feel more alert and improved their quality of life.

This trial is designed to measure the quality of life in response to taking the novel supplement. People over 50 years of age with difficulty sleeping frequently feel tired and lack in energy which degrades their quality of life. We will test the effect of the dietary herbal supplement on quality of life using a validated questionnaire in humans with difficulty sleeping over 50 years of age compared to a placebo in a crossover trial

comparing the supplement to a placebo after 1 week of administration separated by a 2-week washout period.

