The dietary herbal supplement comes in a liquid that is dissolved in flavored water and administered orally in the evening in a 1.79 ounce portion an hour or two before bedtime. Uncontrolled pilot data was generated in 12 people suffering from trouble sleeping who took the dietary herbal supplement for 1 week. They awoke refreshed, felt more alert and felt that the quality of their lives had improved on the supplement. This study will evaluate quality of life in a controlled crossover trial using a validated quality of life measure (1). Since the participants in the pilot clinical trial all had trouble sleeping, we want to understand the safety of the supplement in people with sleep problems, and we also want to understand as much as possible the nature of the sleep difficulty and how the sleep difficulty is related to the stated improvement in quality of life. The polysomnography is the test that allows the determination of the characteristics of the sleep difficulty and the questionnaires are also helpful in determining in what way the quality of life is improved, if the controlled trial confirms the findings of the pilot uncontrolled trial.

Inclusion and Exclusion Criteria

Subjects will be recruited through the Pennington Recruiting Department

Subjects who meet the following criteria will be included in the study.

1. Healthy male or female subjects
2. 50 years of age or older
3. Willing to have blood stored for future research.
4. Usual bedtime between 9 pm and mid-night
5. Chronic difficulty sleeping (trouble sleeping on average for more than 3 nights per week, meeting the International Classification of Sleep Difficulty (ICSD-2*) for at least 6 months.
6. Insomnia Severity Index score greater than or equal to 10 and a minimum of 30 minutes of either sleep-onset latency (SL) or wake after sleep onset (WASO).
7. *ICSD-2 general criteria for sleep difficulty:
 - A. A complaint of difficulty initiating sleep, difficulty maintaining sleep, or waking up too early, or sleep that is chronically non-restorative or poor in quality.
 - B. The above sleep difficulty occurs despite adequate opportunity and circumstances for sleep.
 - C. At least one of the following forms of daytime impairment related to the nighttime sleep difficulty is reported by the patient:
 - a. Fatigue or malaise.
 - b. Attention, concentration, or memory impairment.
 - c. Social or vocational dysfunction or poor school performance.
 - d. Mood disturbance or irritability.

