Subjects will have a screening visit and home oximetry to rule out sleep apnea. Sleep apnea is characterized by episodes in which people stop breathing during sleep. During this cessation of breathing the oxygen in the blood decreases and the lowered oxygen awakens the person. A pulse oximeter is a device that measures the oxygen in the blood stream. If the person experiences drops in blood oxygen during the night, it would be consistent with the person having sleep apnea. If someone screened for the study has episodes of low blood oxygen as measured by the pulse oximeter, they will be referred to their primary physician or a sleep specialist to have a formal sleep study, using polysomnography. That test can not only diagnose sleep apnea, but also define whether there is need for treatment of sleep apnea. Sleep apnea is treated with Continuous Positive Airway Pressure (CPAP). Subjects meeting the inclusion and exclusion criteria will have questionnaires, blood testing and polysomnography and then start one week of a dietary herbal supplement or placebo. The testing done on test day one will be repeated after 1 week. After a 2-week washout period, the same procedures will be repeated at baseline that were performed on week-1. The supplement or placebo not given in the first testing period will be given in the 1-week testing period.

Schedule of Events

Week	Scr	Base	1	3	4
Consent	x				
Medical Questionnaire	x				
Vital signs	x	x	x	x	x
Height	x				
Weight	x	x	x	x	x
Polysomnography		x	x	x	x
Oximetry (R/O Sleep Apnea)	x				
Chubon Quality of Life Rating		x	x	x	x
Insomnia Severity Index	x	x	x	x	x
Epworth Sleepiness Scale		x	x	x	x
Pittsburgh Sleep Quality Index		x	x	x	x
Multidimensional fatigue Inventory	x	x	x	x	x
7-Day Actigraphy &Sleep Diary	x	x		x	
Actigraphy During Sleep Test		x	x	x	x
Chemistry Panel, CBC	x		x		x
Janus kinase 3,			x		x
Archive Serum and Buffy Coat			x		x
Adverse Events			x		x
Dispense/collect Test material	x	x	x	x	

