Screening visit: Subjects will come to the screening visit having fasted for 10 hours except for water. Subjects will give informed consent, have vital signs height and weight measured, have blood drawn for a chemistry panel, CBC, complete a health questionnaire and complete the validated questionnaire, the Insomnia Severity Index. Subjects will have overnight oximetry to screen for sleep apnea rather than true difficulty sleeping. Subjects will be asked to wear an actigraphy to measure motion/activity during the day and night for 7 days. Subjects will be asked to keep a sleep diary for 7 days and return the diary, along with the actigraphy to the study staff for review. Those passing the screening visit will return for study visit one.

Study visit 1: Subjects will come to the sleep lab at 7:00 pm after having eaten dinner at home for an overnight polysomnography test that includes oximetry and actigraphy. Subjects will be asked to sleep from 10:00 pm to 6:00 am the next day. The following morning subjects will complete 5 validated questionnaires: the Insomnia Severity Index, the Epworth Sleepiness Scale, the Pittsburgh Sleep Quality Index, the Chubon Quality of Life Rating Scale, and the Multi-dimensional Fatigue Inventory. Unless a specific cause like sleep apnea is identified as the reason for the fatigue symptoms, the subjects will be given a week's supply of the dietary supplement or placebo with instructions to take 2 ounces an hour before bedtime. The study order of the supplement or placebo will be assigned randomly. Subjects will be asked to use actigraphy and keep a sleep diary for the 7-day period until their next visit.

Study Visit 2: The subject will return in 1 week (± 3 days) for a repeat polysomnography test, 1 hour before which the subject will take the assigned study supplement or placebo. Upon awakening the next morning, the subjects will have a blood drawn for a chemistry panel, a CBC and Janus kinase 3. Subjects will also have blood drawn to archive serum, buffy coat and EDTA plasma. On awakening the next morning they will be asked to complete the 5 validated questionnaires: Insomnia Severity Index, the Epworth Sleepiness Scale, the Pittsburgh Sleep Quality Index, the Chubon Quality of Life Rating Scale and the Multi-dimensional Fatigue Inventory.

After a **2-week washout period** subjects will return for visit 3.

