Study visit 3: This visit occurs after a 2-week washout period, and is the same as visit 1, only the supplement or placebo will be the one the subject was not assigned at study visit 1 (dietary supplement or placebo).

Study visit 4: This visit is the same as visit 2, and will be the end of the trial.

Blood testing: There is the possibility of infection and/or pain and bruising at the vein on the arm where the needle is inserted. Aseptic (sterile) technique and trained personnel minimize these risks.

Questionnaires: There are no known risks to completing the questionnaires

Measuring height, weight, blood pressure and pulse rate has no known risks

Actigraphy is wearing a wrist watch-like device that measures motion. Actigraphy has no known risks

Sleep Diary is to keep track of your sleep habits and experiences. There are no known risks in keeping a sleep diary.

Oximetry is a device that is worn on the finger like a thimble and measures the oxygen in your blood using a light. There are no known risks to wearing an oximetry device

Dietary Supplement is a mixture of 3 foods, a component of chicory, decaffeinated green tea powder and another component of green tea. The supplement has no known risks.

Ingredients: each bottle contains a mixture of 5 grams of collagen peptides, 5 grams of green tea extract, 1 gram of chicory extract, 7 grams of sweetener (half sugar and half erythritol), 0.2% potassium sorbate (as a preservative, 0.1% flavor, 60ml boiling water is added and cooled to 185 degrees F. 53 ml or 1.79 ounces is hot packed in a seal proof bottle that can be stored at room temperature or under refrigeration in this ready to serve format.

Dose: The total volume of each bottle is 53mL or 1.79 ounces and each bottle is one dose

Lot number: The lot number is 2008-1 for the supplement and 2008-2 for the placebo. The supplement and placebo were prepared on August 17, 2020

Preparation: The supplement and the placebo were prepared at the LSU Food Incubator.

Temperature: The supplement and placebo have been stored at room temperature.

Shelf-life: The shelf-life of the supplement is at least 2 years at room temperature. The product was hot packed and contains potassium sorbate which is a preservative for long-term storage. The expiration date for the supplement and placebo is August 17, 2022 and it is presently being stored in the Pennington pharmacy. The results of the stability study are attached.

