Subjects will be withdrawn from the study should it be determined by the medical investigator that the potential benefits of the study are out-weighed by side effects. Subjects may also be withdrawn from the study if they are unwilling or unable to comply with the study requirements.

Risks to Subjects

The only foreseeable risks of this study are those associated with drawing blood. There is the possibility of infection and/or pain and bruising at the vein on the arm where the needle is inserted. Aseptic (sterile) technique and trained personnel minimize these risks. The other procedures in this study have no known risks

Potential Benefits to Subjects

The subjects in this study may experience an improvement in their quality of life in the week they take the supplement. If that does occur, the effect is likely to go away after they are off the supplement for a day or two.

Vulnerable Populations

This study excludes vulnerable populations

Multi-Site Research

This is a single site study.

Sharing of Results with Subjects

The study findings will be shared with the study participants. We are expecting to present the study at a medical meeting and will share the abstract or press release with the study participants. The tests done in the study will be shared with the subjects and with their medical practitioner, if the patient wants that sharing to take place.

Setting

Page 7 of 9

The study will take place at the Pennington Center. Pennington coordinators and other health professionals are well-trained to conduct the procedures in this clinical trial.

Resources Available

We have done a study in which we recruited subjects with sleep difficulty. We have also developed a good relationship with [name], a sleep specialist. Between the patients with sleep problems wanting to enroll through information released by the Pennington Center and our relationship with the Sleep Center, we do not think that gathering study participants for the study will be difficult. Pennington has all the resources needed for this study.

Prior Approvals

We have received approval from the LIFT program with funding to complete the study.

Compensation

Participants will receive \$200 for completing the study.

Confidentiality

The study data will be stored indefinitely at Pennington in the database and in the medical records area. The data will be controlled by the Research Computing Group, and they will be responsible for any data transfer.

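### No adverse-event contact is scheduled after visit 4, and the protocol is inconsistent on whether adverse events are asked about at week 3

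*Combined protocol and SAP*

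**What the plan says.** **End of trial.** Under Procedures Involved, the text for study visit 4 reads: "This visit is the same as visit 2, and will be the end of the trial". Visit 2 is the template. The subject returns "for a repeat polysomnography test, 1 hour before which the subject will take the assigned study supplement or placebo", and on waking has blood drawn and completes the questionnaires. The Schedule of Events stops at week 4.

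**Adverse-event enquiries.** In the Schedule of Events the row "Adverse Events" is marked at weeks 1 and 4 (visits 2 and 4). Screening, baseline and week 3 are blank. The visit-3 text makes that visit a repeat of visit 1 apart from the product given, and visit 1 has no adverse-event mark.

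**Text pointing the other way.** Specific Aim 2 sets out to "Compare the safety of the supplement by evaluating questionnaires, chemistry panel, CBC, Janus 3, adverse events and polysomnography". The rest of that sentence places these measurements at baseline and after the week of dosing, on both sides of the washout. The Procedures Involved narrative says that after the washout "the same procedures will be repeated at baseline that were performed on week-1".

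**Other safety text.** Adverse events are the eighth secondary safety endpoint. The monitoring section has the investigators in contact with the coordinator, partly to learn of worrying side effects, but sets no times. The injury section refers an injured or ill subject for treatment. Risks to Subjects names infection, pain and bruising from the blood draw as the only foreseeable risks.

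**The concern.** Adverse events are part of Aim 2, and little is known about the product's safety: the protocol cites uncontrolled pilot data in 12 people over 1 week and says that no controlled trials exist. Two gaps follow.

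- **After visit 4.** The trial closes on the morning after the last dose and straight after a blood draw. An event that starts later has no scheduled point at which it would be asked about. That includes an infection at the draw site, a risk the protocol itself names.
- **During the washout.** If the schedule governs, nobody is asked at week 3. An event that began off the first product is then first asked about at week 4, when the subject has just spent a week on the second product. No recall period is stated, so it would be unclear which product or period the event belongs to.

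At stake are late events in individual subjects and the attribution of washout events. The primary endpoint is not affected.

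**Working it through.** The plan gives no figure to reproduce. The check reads the schedule against the text, counts enquiries and works out intervals.

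**1. Is the adverse-event row read correctly?** Read by the same columns, the chemistry and CBC row gives screening, week 1 and week 4. That matches the blood draws in the text for screening and visit 2 (and so visit 4). The alignment is sound, and the adverse-event marks are at weeks 1 and 4.

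**2. Week 3, source against source.**

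| Source | Adverse events at week 3? |
|---|---|
| Specific Aim 2 | Implied: names adverse events, at baseline around the washout |
| Procedures Involved narrative | Implied: repeats week-1 procedures, without naming adverse events |
| Schedule of Events | No: cell blank |
| Visit 3 text | No: copies visit 1, which has no mark |

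Neither side settles it. Aim 2 also lists chemistry, CBC and Janus 3, and the schedule has none of these at week 3, so the timing in the aim may be loose. This is an internal inconsistency.

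**3. Enquiries per subject once dosing has begun.**

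| | Schedule followed | Aim 2 followed | With the fix |
|---|---|---|---|
| Weeks 1 and 4 (end of dosing) | 2 | 2 | 2 |
| Week 3 (off first product) | 0 | 1 | 1 |
| After visit 4 (off second product) | 0 | 0 | 1 |
| Per subject | 2 | 3 | 4 |
| 10 completers | 2 × 10 = 20 | 3 × 10 = 30 | 4 × 10 = 40 |

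The zero after visit 4 is the same on both readings.

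**4. Last dose to the final morning.** The visit-1 text gives the clock times: "Subjects will be asked to sleep from 10:00 pm to 6:00 am the next day". With a dose 1 hour before a 10 pm start, 9 pm to 6 am is 9 hours. The Background allows the product to be "administered orally in the evening in a 1.79 ounce portion an hour or two before bedtime"; a dose 2 hours before gives 8 pm to 6 am, or 10 hours. The visit text is the more specific, so about 9 hours is the working figure. It assumes that the visit-1 times apply at visit 4 and that the enquiry is made in the morning; the visit text does not say when in the visit it is made.

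**5. First product's last dose to the next enquiry.**
- Schedule followed: week 1 to week 4 is 3 × 7 = 21 days, or 18 to 24 with the ±3-day window carried from visit 2 to visit 4.
- Enquiry at week 3: 2 × 7 = 14 days.

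**6. Who is affected.** The missing contact after visit 4 applies to all 10 subjects for the blood draw. For the supplement itself it applies to those who take it second: about 5 of 10 if the orders are balanced. Balance is an assumption, because the protocol says only that order is random.

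**7. Participation after baseline.** Now 4 × 7 = 28 days; with a call 14 days after visit 4, 28 + 14 = 42 days, or 6 weeks.

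**The case against.** The case for leaving the plan alone has real content.

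- **Week 3 may be only a missing mark.** Aim 2 names adverse events around the washout and the narrative leans the same way. This stands. A reader of the schedule alone might infer that neither product has any off-treatment enquiry; the documents do not support that as a settled fact. But the inconsistency still needs resolving, because visit staff may well work from the schedule.
- **Washout events need not be lost.** Subjects attend at week 3 for vital signs, polysomnography and questionnaires, and nothing limits the week-4 question to the preceding week. This also stands. Recall may recover such events, though after a week on the other product.
- **Monitoring text exists.** It does concern participants' side effects. It is untimed and schedules no contact with a subject. The consent pages are not in the copy reviewed, so what subjects are told about reporting late problems is unknown; the claim is only that no contact is scheduled.
- **The risk is low.** The trial is a ten-subject pilot, described as minimal risk, with a week of each product and no delayed product harm named. A reader might take the protocol's remark that "the effect is likely to go away after they are off the supplement for a day or two" as the period in which harm could still occur. It describes quality-of-life benefit and does not measure a safety risk.
- **Two weeks is a convention.** It is taken from the washout, not from any known timing of harm, and one enquiry would be in person and the other by telephone. Both points stand; the match between products is approximate.

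**Conclusion.** The point holds in two parts of unequal certainty. No adverse-event contact is scheduled after visit 4; that is clear on any reading of the available text. Adverse-event collection at week 3 is inconsistent between Aim 2 and the narrative on one side, and the schedule and visit-3 text on the other.

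The size is small. Scheduled off-treatment enquiries number 0 or 1 per subject, depending on which text is followed, against 2 with the fix. If the schedule is followed, the first enquiry after the first product's washout comes about 21 days (18 to 24) after its last dose.

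A reader might infer that the safety comparison in Aim 2 is biased. The documents do not support that: in both orders each product has a marked enquiry at the end of its own dosing week, so the on-treatment comparison is even. What is uncertain is late events and the attribution of washout events.

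This is an optional patient-safety improvement. It rests on the schedule columns being read correctly, which the chemistry row supports, and on the removed consent pages not setting up a contact.

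**What to change.** 1. Mark adverse events at week 3 in the Schedule of Events, and state in the visit-3 text that the question is asked before the second product is dispensed. This also brings the schedule into line with Aim 2 on adverse events.
2. Add a column after week 4 for one telephone adverse-event contact by the existing coordinator, about 2 weeks after visit 4.

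Make both changes together. Each product then has an off-treatment enquiry at about 14 days in both orders; a call after visit 4 alone, with week 3 left blank, would give that enquiry only to whichever product came second.

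**Cost.** About 10 short calls, 10 enquiries at a visit subjects already attend, and a protocol and consent modification. Participation becomes about 6 weeks instead of about one month. The Chubon endpoint is complete at visit 4, so the last call can fall within the planned 2-week analysis period and before the 4-week report. If study completion is counted from the last call, both dates move by 2 weeks.

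A timed medical review of the visit-4 chemistry and CBC is a separate minor matter, and this change does not depend on it.

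### Does the instruction to take 2 ounces, when one dose is defined as a 53 mL (1.79 oz) bottle, call for a change to the plan?

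*Combined protocol and SAP*

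**What the plan says.** The protocol gives the nightly amount in four places.

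- **Background:** the supplement is "administered orally in the evening in a 1.79 ounce portion".
- **Procedures Involved, Dose entry:** "The total volume of each bottle is 53mL or 1.79 ounces and each bottle is one dose".
- **Procedures Involved, Ingredients entry:** the fill is the same, in a ready-to-serve bottle: "60ml boiling water is added and cooled to 185 degrees F. 53 ml or 1.79 ounces is hot packed".
- **Procedures Involved, Study visit 1:** "the subjects will be given a week's supply of the dietary supplement or placebo with instructions to take 2 ounces an hour before bedtime".

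Study visit 3 carries the last of these into the second period: "This visit occurs after a 2-week washout period, and is the same as visit 1", apart from the switch of product.

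On composition, the Dietary Supplement entry reads "Dietary Supplement is a mixture of 3 foods, a component of chicory, decaffeinated green tea powder and another component of green tea" and continues "The supplement has no known risks". The Ingredients entry that follows says "each bottle contains a mixture of 5 grams of collagen peptides, 5 grams of green tea extract, 1 gram of chicory extract", then lists sweetener, preservative and flavor.

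**The concern.** An instruction to subjects should match the dose unit that the protocol defines. Here one bottle cannot supply the stated 2 ounces if the words are taken literally. A subject would have to open a second bottle each night, or would fall short of the instruction while taking exactly one defined dose. If subjects read it differently from one another, the amount taken could vary, and staff checking returned test material would have two possible nightly amounts to check against.

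The composition point looks awkward for a different reason. A list of three foods, placed beside a statement about risk, omits an ingredient that equals the green tea extract in weight (5 g each) and is five times the chicory extract (1 g).

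**Working it through.** **Inputs.** Bottle: 53 mL = 1.79 oz (Dose and Ingredients entries). Instruction: 2 oz (Study visit 1, repeated at Study visit 3). Assumed conversion: 1 US fluid ounce = 29.5735 mL.

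**1. Reproduce the protocol's own figure.** 53 / 29.5735 = 1.792, which agrees with the stated 1.79. The imperial ounce (28.4131 mL) would give 53 / 28.4131 = 1.865, which does not agree. The protocol's ounce is therefore the US fluid ounce, and its arithmetic is correct.

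**2. Size of the mismatch.** 2 × 29.5735 = 59.15 mL. Then 59.15 − 53 = 6.15 mL, and 59.15 / 53 = 1.116, an excess of 11.6%. The protocol's own ratio gives nearly the same: 2 / 1.79 = 1.117.

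**3. Can the two figures be read together?** Rounded to a whole ounce, 1.79 is 2. A weight reading is also numerically possible: two avoirdupois ounces are 2 × 28.3495 = 56.70 g, and 56.70 / 53 = 1.07 g/mL. The listed recipe has 5 + 5 + 1 + 7 = 18 g of solids in 60 mL of water. If the solids occupy 0.6 to 0.7 mL/g (an assumption), its density is 78 / 70.8 = 1.10 down to 78 / 72.6 = 1.07 g/mL. The protocol states neither reading. Rounding is the simpler one.

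**4. Is there a shortfall over the week?** With seven nights and seven bottles, the literal instruction needs 7 × 59.15 = 414 mL against 7 × 53 = 371 mL. That is 43 mL short, with enough for 371 / 59.15 = 6.3 nights. The result depends on the literal reading and on a bottle count that the protocol never gives. Study visit 2 falls at 1 week ± 3 days (4 to 10 days) and has its own dose before polysomnography, so seven nights is not fixed either. No shortfall can be claimed.

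**5. Does the comparison move?** The analysis is a paired t-test of supplement against placebo in ten subjects, and the protocol makes no power calculation. Volume enters none of this. The instruction is the same for both products and both periods. As a bound, suppose the effect were proportional to volume and a fraction f of subjects took the literal 2 oz. The mean effect would then be multiplied by 1 + 0.116f, between 1.00 (f = 0) and 1.116 (f = 1). Its sign could not change.

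**6. Two side points.** The recipe adds 60 mL of water and packs 53 mL, a difference of 7 mL. Loss between boiling and hot filling may account for some of this, and the text does not say whether the grams are per mix or per packed bottle, so it is not a contradiction. The Background sentence naming chicory and green tea also omits collagen, but it is not an exhaustive list, and collagen peptides come first among the six candidate components named just before it. Only the three-foods sentence conflicts with the Ingredients entry.

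**The case for a change.** The strongest case for acting is that the rounded figure sits in the sentence describing what subjects are told, while the two-decimal figure sits in the product description. Nothing in the protocol says that 2 ounces is rounded, and the Study visit 1 text does not mention a bottle. The Schedule of Events has test material dispensed and collected, so a nightly amount is needed for checking returns. Correcting the wording would be cheap, and an ingredient list beside a risk statement ought to be complete.

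Much of this stands. The wording does conflict, and the dose passages must be reconciled. It does not follow that the protocol lacks a dose definition: the Dose entry is explicit and agrees with the Background portion and the fill volume. Nor does it follow that anyone would be misdosed, since the bottle label and the participants' instructions cannot be seen. The collagen omission is corrected by the paragraph that comes straight after it, and no risk specific to collagen is in question.

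**Conclusion.** The mismatch is real but clerical: 6.1 mL, or 11.6%, between one visit narrative and three statements that agree with one another, plus one incomplete product description. The Study visit 1 and 3 instruction must be reconciled in wording with the Background, Dose and Ingredients statements. Which volume should stand is for the sponsor to settle, and this review takes no position on it.

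No change to the design, sample size, endpoints or analysis follows, because none of them uses the volume and the instruction is common to both products and both periods. The conclusion rests on the US fluid ounce, which the protocol's own conversion supports, and on 2 ounces being most plausibly a rounded figure for a single-serve bottle. If that second assumption is wrong, the difference is still at most 11.6% in amount, and the supplement-placebo comparison remains valid for the dose actually taken.

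### A week's supply does not cover on-treatment visits up to 3 days late, so doses can lapse before the primary assessment; the 2-ounce instruction also mismatches the 53 mL dose

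*Combined protocol and SAP*

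**What the plan says.** **Dose.** The Dose paragraph under Procedures Involved states: "The total volume of each bottle is 53mL or 1.79 ounces and each bottle is one dose". The Background agrees, describing a product "administered orally in the evening in a 1.79 ounce portion an hour or two before bedtime". The instruction actually given to subjects differs. Under Study visit 1, unless a specific cause such as sleep apnea is found, "the subjects will be given a week's supply of the dietary supplement or placebo with instructions to take 2 ounces an hour before bedtime". Study visit 3 repeats visit 1 with the other product.

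**Timing.** The paragraph on the second visit sets both the window and a dose shortly before the test: "The subject will return in 1 week (± 3 days) for a repeat polysomnography test, 1 hour before which the subject will take" that period's product. For the primary outcome the same paragraph says "On awakening the next morning they will be asked to complete the 5 validated questionnaires", and the Chubon scale is one of the five. Of visit 4 the protocol says "This visit is the same as visit 2, and will be the end of the trial", so the 3-day tolerance applies in both periods.

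**Persistence of effect.** Potential Benefits to Subjects says of any improvement that "the effect is likely to go away after they are off the supplement for a day or two".

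**Accountability.** The Schedule of Events has a row "Dispense/collect Test material", which in the available text is marked at screening, baseline, week 1 and week 3. The protocol gives no number of bottles per subject, no spare bottles, no rule for dosing after the seventh night when a visit is late, and no record of bottles returned or of the last dose.

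**The concern.** Two parts of the dosing plan do not fit together.

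The first is the amount. The instruction to subjects is for more than a bottle holds, although one bottle is defined as one dose.

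The second has more consequence. The amount dispensed is set for one week, while the interval it must cover can be three days longer. The primary endpoint is scored on the morning that ends this interval, so any lapse falls immediately before the measurement or one dose before it. By the protocol's own expectation, a lapse of a day or two may be enough for the effect to disappear.

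Supplement and placebo are to be compared by paired t-test in ten subjects. If the supplement works, a subject who has run out contributes a smaller difference than the treatment would have produced. Under Power analysis, a non-significant result is to be the basis for powering a definitive trial, so a diluted estimate would carry into that calculation.

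**Working it through.** **Inputs.** Bottle: 53 mL, stated as 1.79 ounces (Dose). Instruction: 2 ounces (Study visit 1). Supply: one week (Study visit 1). Return: 1 week ± 3 days, with a dose 1 hour before the test (Study Visit 2). Subjects: ten (Number of Subjects). Assumed, because not stated: seven bottles per period, one taken every evening from dispensing.

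**Step 1: the plan's own conversion.** With 29.57 mL to the US fluid ounce, 53 / 29.57 = 1.79 ounces. The stated figure is correct. In imperial ounces it would be 1.87, so US units are meant.

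**Step 2: instruction against bottle.** 2 × 29.57 = 59.1 mL. The excess over one bottle is 59.1 − 53 = 6.1 mL, and 59.1 / 53 = 1.116, or 11.6% more.

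**Step 3: doses due against supply.** Visit 1 is an overnight visit and product is handed out the next morning, so the first dose is that evening. If visit 2 takes place d days after the visit 1 night, d doses are due, counting the one before polysomnography. Nights without product are max(0, d − 7) if every dose comes from the take-home supply, and max(0, d − 1 − 7) if the site supplies the polysomnography-night dose.

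| Visit night, d | Doses due | Nights without product, all from take-home supply | Nights without product, test-night dose on site |
|---|---|---|---|
| 7 | 7 | 0 | 0 |
| 8 | 8 | 1 | 0 |
| 9 | 9 | 2 | 1 |
| 10 | 10 | 3 | 2 |

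If the week is counted from the dispensing morning instead, each row needs one more dose: 8 on schedule and 11 at +3 days. Each shortfall then rises by one, except that the on-schedule visit still has none if the test-night dose is given on site.

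**Step 4: where the gap falls.** In the third column the missed nights run up to and include the night before the Chubon scale. In the fourth column the subject misses up to two nights, takes one dose in the sleep lab and completes the scale the next morning.

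**Step 5: effect on the comparison.** Suppose k of ten subjects have a gap in the supplement period and each loses a fraction f of a common effect. The expected mean difference is then multiplied by 1 − kf/10. One subject losing everything removes 10% of it; one losing half removes 5%. A gap in the placebo period removes no active ingredient. The documents give neither k nor f, nor the effect itself, so this gives the direction and the weight per subject, not a forecast.

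**The case against.** The best reply on the dose is that 2 ounces is simply 1.79 rounded up. The bottle is sealed, ready to drink and defined as one dose, and nothing in the protocol mentions measuring or splitting bottles. That stands. A reader might infer that subjects would open a second bottle each night for 6.1 mL and reach the seventh night with only 7 × 53 − 6 × 59.15 = 16 mL. The documents do not support that as the likely course; most subjects would drink one bottle.

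On supply, the reply is that neither the bottle count nor the source of the polysomnography-night dose is stated. The subject takes that dose 1 hour before the test, so it may well be given in the sleep lab, and the schedule row for test material is marked at week 1. This stands in part. On-site dosing removes the gap for a visit one day late and ensures a dose on the evening before the Chubon scale. It does not remove the one or two missed nights for visits two or three days late. If more than seven bottles are dispensed the gap may vanish, but the protocol does not say so.

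A reader might also infer a large loss of power. That would require an assumed effect size, an assumed number of late visits and complete loss of effect in each affected subject. The documents give neither of the first two. On the third, they say only that the effect is likely to go after a day or two off product, which does not establish complete loss after one missed night or when a dose precedes the assessment.

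Finally, the absence of a week-4 mark in the test-material row might suggest that second-period intake cannot be reconstructed. That goes too far. A mark at screening makes little sense, because product is first given after visit 1. Moved one column to the right, the row would show the expected pattern, and visit 4 is said to repeat visit 2. The missing mark may be a typing or table-reading fault. What the text does lack is any stated bottle count or last-dose date.

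**Conclusion.** The concern holds in a limited form, and the plan should be changed. The mismatch between 2 ounces and 53 mL is a wording error, probably rounding, and has little consequence if subjects drink one bottle.

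The supply gap is real on the text. With seven bottles and one bottle a night, a subject seen on days 8 to 10 is without product for 1 to 3 nights before the primary assessment, or 0 to 2 nights if the test-night dose is supplied on site. Counting from the dispensing morning adds one night to each figure. If the supplement has an effect that fades as the protocol expects, such gaps in the supplement period bias the paired difference toward zero. Each affected subject carries one tenth of the mean.

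The overall size cannot be stated, and it is zero if no supplement-period visit runs late or if enough bottles are in fact given. No stated sample size, power or significance level is affected, because the protocol calculates none.

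**What to change.** At visits 1 and 3, instruct subjects to take one whole 53 mL bottle each evening, and delete the 2-ounce wording. State the number of bottles dispensed and whether the polysomnography-night dose comes from the take-home supply or from the site.

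Then do one of the following:

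- Dispense enough for the longest interval: 10 bottles per period, or 11 if the week is counted from the dispensing morning.
- Keep the supply at one week and restrict visits 2 and 4 to -3/+0 days, with the week counted from the visit 1 night.

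In either case, record the number of bottles returned and the date of the last dose at visits 2 and 4, and check that the schedule row for test material is marked at week 4.

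The first option costs 3 to 4 extra bottles × 2 periods × 10 subjects = 60 to 80 bottles, half of them placebo. The remaining stock is not stated. It also lets a late subject have up to 10 or 11 nights of exposure instead of 7, which should be reported. The second option needs no extra product but makes sleep-lab booking less flexible. The design, sample size and paired analysis are unchanged under either.
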